1.5 Clinical Data - Prostate

Two basic ultrasound technologies have been used to image microbubble contrast agents in the prostate: Doppler and grayscale HI. These technologies are summarized in a textbook by one of the PIs.⁵² Color and power Doppler imaging techniques, available on most modern ultrasound systems, utilize relatively high energy levels that destroy a large proportion of the microbubbles as they are imaged. Pulse inversion and grayscale HI are technological advances that together permit high resolution, low energy grayscale imaging of contrast agents.^{53,54,55,56} Various pulsing sequences can further improve grayscale HI of the prostatic microcirculation.^{57,58} Flash replenishment imaging was first described as a grayscale harmonic technique that can demonstrate tissue perfusion and may be used for blood flow estimation.^{59,60,61} Contrast-Enhanced Flash Replenishment may be combined with Maximum Intensity Projection (CE-FR-MIP) of each pixel in the image over 2-4 seconds of low power image frames to demonstrate microvascular patterns associated with neovascularity⁶² and PCa.⁶³ Whereas assessment for neovascularity with contrast-enhanced Doppler imaging is based upon the magnitude of contrast enhancement, CE-FR-MIP provides additional information based upon changes to the normal intraprostatic microvascular architecture (Fig. 4).

[figure not shown]

Figure 4. Gleason 7 PCa in the right mid-gland is invisible on grayscale (left image), but tumor vascularity is clearly defined with CE-FR-MIP imaging (right image; arrows).

Numerous trials of CE-TRUS using HI to detect PCa have been conducted at the Jefferson Prostate Diagnostic Center.^{64,65} An early study ($n=100$ subjects) demonstrated improved sensitivity for PCa detection from 38% at baseline to

65% after infusion of the microbubble agent Definity (Lantheus Medical Imaging, N Billerica, MA); $p \leq 0.004$.⁶⁶ Furthermore, lesions detected by contrast-enhancement were generally larger and with a higher Gleason score – that is, they were the more clinically significant cancers. The last 40 subjects in this study were evaluated with targeted biopsy. A suspicious site identified by CE-TRUS was 3.5 times more likely to have a positive biopsy than an adjacent site without contrast enhancement ($p < 0.025$).⁶⁷

A Department of Defense funded clinical trial of 301 men demonstrated that targeted cores based upon CE-TRUS were twice as likely to return a positive biopsy as systematic cores.⁶⁸ Using CE-FR-MIP, our group demonstrated positive biopsies in 29/225 targeted cores as compared with 50/600 systematic cores, yielding an odds ratio of 2.0 for cancer detection with CE-TRUS ($p = 0.034$).⁶⁹ A recently completed National Cancer Institute (NCI) funded clinical trial ($n = 272$) confirmed increased PCa detection with CE-TRUS, and specifically with CE-FR-MIP (OR=2.1, $p < 0.001$). More significantly, CE-TRUS preferentially detected lesions with greater tumor volume and Gleason score ≥ 7 ($p < 0.001$). ROC analysis for detection of high volume / high grade PCa with CE-TRUS yielded an area under the curve of 0.90 ($p = 0.001$).⁷⁰ Comparison of CE-TRUS HI with whole mount prostatectomy specimens in our DOD and NCI study subjects demonstrated microbubble enhancement in 93% of malignant foci. In summary, PCa's visualized with CE-TRUS tend to be larger and of higher grade.

In summary, clinical studies demonstrate selective detection of higher grade PCa with HI, based upon the increased neovascularity of these tumors. Nonetheless, although CE-TRUS with HI selectively detects clinically significant PCa, overall by-patient detection of high grade PCa with targeted biopsy based upon HI alone remains inferior to a 12 core systematic biopsy. This limitation is related, in part, to difficulty discerning enhancing foci of PCa adjacent to the hypervascular transition zone (see abstract in appendix). A major limitation of HI is related to reduced blood-to-tissue contrast resulting from second harmonic generation and accumulation in tissue.⁷¹ Hence, subharmonic imaging (SHI), transmitting at the fundamental frequency (f_0) and receiving at the subharmonic ($f_0/2$), becomes an attractive alternative contrast-specific imaging mode, because of the weaker subharmonic generation in tissue and the significant subharmonic scattering produced by some new contrast agents.⁷² As demonstrated in the previous section, preliminary data with SHI suggest that this technique provides a superior signal to background ratio for evaluation of blood flow, that SHI can improve depiction of neovessels, and that SHI may be useful for quantitative assessment of tissue perfusion in cancer. In order to optimize the detection of clinically significant PCa, we propose the use of SHI with CE-TRUS for targeted biopsy of the prostate.

1.6 Dose Rationale and Risk/Benefits

Based upon our previous experience with Definity and according to the package insert, two vials of Definity will be mixed and diluted in 50 ml of normal saline, yielding a concentration of 49.4 $\mu\text{l/ml}$. For the purpose of contrast-enhanced imaging, Definity will be infused over approximately 10-12 minutes, during which time pulse inversion HI and SHI will be performed. Definity remains stable within the circulation for 3 to 6 minutes after infusion; all contrast-enhanced procedures will be completed during the infusion time. The risk of this procedure is basically the risk of an adverse reaction to Definity. The largest safety studies published to date on the use of ultrasound contrast agents in humans (involving up to 4,300,966 subjects) concluded that these agents have a good safety profile in both cardiac and non-cardiac applications.^{73,74,75,76} In our experience, adverse reactions to Definity include only minor sensations of discomfort which resolve as soon as the infusion is stopped.

2.0 STUDY OBJECTIVES

1. To implement SHI technology on a transrectal probe suitable for prostate imaging and biopsy
2. To demonstrate visualization of prostatic vascularity during subharmonic contrast enhanced imaging of the prostate.
3. To provide a preliminary estimate of the diagnostic accuracy of contrast-enhanced subharmonic imaging for detection of prostate cancer.

3.0 STUDY DESIGN

3.1 General Design

This study is a pilot phase II clinical trial of 55 patients (5 controls and 50 patients) over the course of 2 years. Experimental software used for subharmonic imaging of other body parts will be adopted to work with the transrectal prostate probe of an FDA approved ultrasound system, specifically the IC5-9D transducer on the Logiq E9 system (GE Healthcare; Milwaukee, WI). In vitro testing will be performed on 5 patients to ensure that the power output of the transducer with the new subharmonic software is within the FDA approved limits for the system power output. After in vitro optimization of the subharmonic mode for imaging, we will conduct a pilot clinical trial of 50 patients over 2 years. All participants will be evaluated with contrast-enhanced transrectal ultrasound (CE-TRUS) prior to prostate biopsy. Subharmonic imaging of the CE-TRUS study will be used to direct targeted biopsy of the prostate with up to 6 biopsy cores. This will be followed by a conventional systematic biopsy of the prostate with 12 cores.

3.2 Primary Study Endpoints

- a. Demonstration of prostate vascularity with subharmonic contrast-enhanced imaging. Specifically, demonstration of increased prostate vascularity in patients with high risk, aggressive prostate cancer.
- b. Preliminary measures of efficacy (sensitivity and specificity) will be obtained for subharmonic CE-TRUS in the detection of high risk, aggressive prostate cancer after biopsy procedure on 50 patients.

3.3 Secondary Study Endpoints

n/a

3.4 Primary Safety Endpoints

No safety issues are expected from the use of subharmonic imaging, as the power output of the ultrasound system will be similar to its operation in conventional mode. No safety issues are expected from the administration of Definity for CEUS, as this agent has been used safely in numerous clinical trials and is FDA approved for intravenous administration during cardiac imaging.

4.0 SUBJECT SELECTION AND WITHDRAWAL

4.1 Inclusion Criteria

1. Subject must be scheduled for a clinically indicated needle biopsy of the prostate based upon an elevated PSA, abnormal digital rectal examination, or based upon active surveillance of prostate cancer.
2. Subject must be able and willing to give written informed consent for a contrast enhanced ultrasound study of the prostate.
3. Subject must be a male at least 18 years of age when informed consent is obtained.
4. Subject must have a life expectancy that exceeds the duration of the clinical trial.

4.2 Exclusion Criteria

1. Participant in a clinical trial involving an investigational drug within the past 30 days.
2. Patients with known or suspected hypersensitivity to perflutren
3. Previous treatment for PCa.
4. Clinically unstable, severely ill, or moribund.

4.3 Gender/Minority/Pediatric Inclusion for Research

This study is only applicable to adult males, as PCa is only present in the adult male population. The study will include men of all races; there will be no exclusion based upon race or ethnicity.

4.4 Subject Recruitment and Screening

Fifty adult male patients will be recruited to this study by our urology co-investigators from the population scheduled to undergo prostate biopsy at Thomas Jefferson University Hospital. Subjects will be screened for eligibility by the attending urologist. The urologist will explain the procedure and may obtain written informed consent from each study participant at that time or in radiology on the day of study and prior to any study procedures being performed.

4.5 Early Withdrawal of Subjects

4.5.1 When and How to Withdraw Subjects

Any subject may withdraw from the study up until the time the CEUS study is performed. However, once that study is performed, the data will be included in our analysis.

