Duration of administration and follow-up	The contrast administration will require 10-15 minutes, during which time a transrectal ultrasound study of the prostate will be performed, and a targeted biopsy procedure of the prostate will be performed.
Reference therapy	Conventional 12-core systematic prostate biopsy
Statistical Methodology	Computation of sensitivity and specificity for detection of clinically significant prostate cancer with conventional 12 core prostate biopsy as the reference standard. No further statistical testing will be performed as this is a preliminary study, designed to demonstrate the feasibility of subharmonic imaging of the prostate and to obtain an estimate of the diagnostic accuracy of CEUS with subharmonic imaging of the prostate.

Schema
	
Subharmonic imaging software will be expanded to work with an endorectal probe on an FDA approved ultrasound imaging system
 
↓
 
Patient with elevated PSA or an abnormal rectal exam, or a patient requiring a prostate biopsy on active surveillance
 
↓
 
Scheduled for prostate biopsy
 
↓
 
Has CEUS with subharmonic imaging
 
↓
 
Prostate biopsy with up to 6 targeted cores based upon subharmonic imaging as well as prostate biopsy with 12 standard systematic cores.

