6.0 STUDY PROCEDURES

6.1 Study Visit Schedule

The CEUS study procedure will be performed during a single episode of care at which time the patient will undergo a clinically indicated biopsy of the prostate. No additional visits will be required to participate in the study.

All ultrasound imaging will be performed with a commercially available Logiq E9 ultrasound system that provides conventional color and power Doppler imaging, and which will be modified to provide contrast-enhanced HI and SHI. Because of the very low SHI signal obtained from tissue, SHI is performed with a dual imaging technique that displays a conventional grayscale image alongside the SHI image. The conventional grayscale image is necessary to define the tissue anatomy and determine location within the prostate while the SHI is used to demonstrate vascularity and neovessels.

The proposed microbubble contrast agent for the current study, Definity®, (Perflutren Lipid Microsphere, Lantheus), is a microbubble contrast agent that demonstrates enhancement of the prostate on both grayscale and Doppler imaging. Definity remains stable within the circulation for 3 to 6 minutes after infusion and all contrast-enhanced procedures will need to be completed during the infusion time. This time constraint has not been a problem in prior studies. Based on our previous experience with Definity (and in accordance with the manufacturer's instructions), two vials will be mixed and diluted in 50 ml of

normal saline, yielding a concentration of 49.4 $\mu\text{l/ml}$. A 20 gauge intravenous catheter will be inserted into an arm vein for administration of contrast material. Definity will be delivered as an infusion at an initial rate of 4 ml/min. The infusion rate will be titrated to achieve adequate enhancement of the prostatic microvasculature. Post contrast imaging will begin as soon as contrast is visible. The infusion of Definity will continue for approximately 10-12 minutes during which time the contrast-enhanced diagnostic ultrasound, the assignment of rating scores, and the SHI guided biopsy procedure will be performed.

[figure not shown]

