7.2 Statistical Methods

Rough estimates of the sensitivity and specificity of SHI for high grade disease may be obtained if there are sufficient patients with high grade disease. No additional statistical analysis will be performed

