7.3 Subject Population(s) for Analysis

All study participants will be included in the analysis.

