9.0 DATA HANDLING AND RECORD KEEPING

9.1 Confidentiality

Information about study subjects will be kept confidential and managed according to the requirements of the Health Insurance Portability and Accountability Act of 1996 (HIPAA). Those regulations require a signed subject authorization informing the subject of the following:

- What protected health information (PHI) will be collected from subjects in this study
- Who will have access to that information and why
- Who will use or disclose that information
- The rights of a research subject to revoke their authorization for use of their PHI.

In the event that a subject revokes authorization to collect or use PHI, the investigator, by regulation, retains the ability to use all information collected prior to the revocation of subject authorization. For subjects that have revoked authorization to collect or use PHI, attempts should be made to obtain permission to collect at least vital status (i.e. that the subject is alive) at the end of their scheduled study period.

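### Section 4.5.1 closes withdrawal at the CEUS although the SHI-targeted research cores may still be to come, and it merges stopping participation with keeping data

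*Combined protocol and SAP*

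**What the plan says.** Section 4.5.1 has two sentences. The first sets the limit on leaving: "Any subject may withdraw from the study up until the time the CEUS study is performed". The second concerns data: "However, once that study is performed, the data will be included in our analysis". No other section describes withdrawal from the study after the scan.

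The order of procedures is given in several places:

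- Section 3.1 has every participant scanned by CE-TRUS before biopsy. The SHI images then direct up to 6 targeted cores, and the 12 systematic cores follow.
- The schema in the Study Summary shows CEUS with SHI as one step and the biopsy, targeted plus systematic, as the next.
- Section 6.1 describes an infusion of about 10-12 minutes "during which time the contrast-enhanced diagnostic ultrasound, the assignment of rating scores, and the SHI guided biopsy procedure will be performed".
- Section 6.2 has the targeted specimens taken while contrast-enhanced imaging is under way.

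Section 9.1 deals with a subject who revokes authorization to use health information. The investigator then "retains the ability to use all information collected prior to the revocation of subject authorization".

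On analysis, Section 7.3 reads: "All study participants will be included in the analysis". Section 7.2 adds: "Rough estimates of the sensitivity and specificity of SHI for high grade disease may be obtained", provided enough men have high-grade disease, and then: "No additional statistical analysis will be performed". The Study Summary computes both measures "with conventional 12 core prostate biopsy as the reference standard".

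**The concern.** The biopsy itself is clinically indicated (Sections 1.3 and 4.1). The targeted cores are different: they exist because of the study, and Section 5.1 says participants may not benefit from the findings. A withdrawal rule should let a man decline those cores up to the moment they are taken. Section 4.5.1 instead fixes the last opportunity at the scan.

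Wanting to stop part-way is not far-fetched. Sections 1.6 and 5.3 report sensations of discomfort with Definity that resolve when the infusion is stopped. A man who has been imaged and wants no more research procedures, and the staff looking after him, cannot tell from the protocol whether he may still leave.

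The second sentence of 4.5.1 compounds this. Placed directly after the cut-off, it reads as the reason for it, as if keeping the data required ending the right to withdraw. It does not. Data already collected can be kept whether or not the subject goes on.

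**Working it through.** The main check is textual, so I set the provisions side by side.

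**1. When does the right to withdraw end?** Section 4.5.1 ends it when the CEUS is performed. It states a rule; it is not silent on the matter.

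**2. Are study procedures still to come at that point?**

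- On the sequence in Section 3.1 and the schema, yes: up to 6 targeted cores, then the 12 systematic cores.
- On Sections 6.1 and 6.2, the targeted cores fall within the infusion and imaging. If performing the CEUS means finishing that whole session, no targeted core remains.

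The two descriptions give different answers, and 4.5.1 does not say which it means.

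**3. Does 4.5.1 agree with 9.1?** If the data in 4.5.1 are the CEUS data, the sections agree: both keep what was collected before the subject left. They diverge only if the word also covers pathology collected after a revocation, which 4.5.1 does not say. The difference that stands is one of structure. Section 9.1 deals with retention without limiting when a subject may act, while 4.5.1 joins the two.

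**4. Whom does 4.5.1 bring into the analysis?** Only men whose CEUS was performed. A consented man who left before the scan is outside it. Section 7.3, read literally, includes him. A sensitivity and specificity table needs an SHI result and a reference result for each man, and no section says what to do when one is missing. Section 9.3 requires only that missing data be explained on the CRF. The 5 controls counted in the Study Summary and Section 3.1 are not mentioned in 7.3 either.

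**5. Would an evaluable set undermine Section 7.1?** Inputs from 7.1: n = 50, high-grade rate p = 0.15, X ~ Binomial(n, p).

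| Quantity at n = 50 | Stated in 7.1 | Recomputed |
|---|---|---|
| Mean, 50 × 0.15 | 7.5 | 7.5 |
| P(X ≥ 5) | 88% | 88.8% |
| P(X ≤ 3) | 4.6% | 4.60% |
| P(X = 0) = 0.85^50 | 0.03% | 0.030% |
| P(X ≥ 3) | greater than 95% | 98.6% |

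The plan's figures reproduce. The documents give no rate of withdrawal or missing biopsy, so the number of non-evaluable men, m, is an assumption. With n = 50 − m:

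| Assumed m | n | P(X ≥ 3) | P(X ≥ 5) |
|---|---|---|---|
| 0 | 50 | 98.6% | 88.8% |
| 2 | 48 | 98.2% | 86.6% |
| 5 | 45 | 97.3% | 82.5% |
| 10 | 40 | 95.1% | 73.7% |

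The statement in 7.1 about at least 3 high-grade men therefore survives up to 10 non-evaluable men of 50; at 11 (n = 39) the probability is 94.5%. The sample size need not change.

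**The case against.** The strongest reply is that 4.5.1 is only a data-retention rule, loosely worded. The scan, scoring and targeted cores form one short session under contrast, so the CEUS study may mean all of it, and then no research core follows the cut-off. Nothing in the protocol says a man must undergo cores that he refuses. Section 11.0 requires a consent form that complies with federal rules. That form is not in the text available here, so what it says on withdrawal cannot be checked.

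Much of this stands. It shows that the timing is ambiguous and that no compulsion is stated. It does not rescue the first sentence of 4.5.1, which still sets a last moment for leaving that the schema and Section 3.1 place before the targeted cores. If only data retention was meant, the sentence should say so.

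A reader might infer more than the documents support:

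- **That 4.5.1 and 7.3 together force men without a scan or without pathology into the accuracy table.** Section 4.5.1 covers only scanned men. No rule assigns a man with a missing result to a cell, so he would ordinarily be left out.
- **That the estimates are therefore biased by a known amount.** Any such figure presupposes an imputation that the plan never prescribes, applied to a number of men that the plan never gives.
- **That 4.5.1 contradicts 9.1.** That requires extending the data in 4.5.1 to later pathology.

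**Conclusion.** The point holds for the withdrawal rule. As written, Section 4.5.1 ends the right to leave once the CEUS is performed, while Section 3.1 and the schema put up to 6 research cores after it. Sections 6.1 and 6.2 allow a milder reading, which makes the cut-off ambiguous rather than sound. The section also merges stopping participation with keeping data, which 9.1 treats separately.

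The gap in 7.3 is secondary: an unstated denominator for the accuracy estimates. I attach no size of bias to it. The only calculation here shows that restricting the accuracy set is affordable. It rests on the 15% high-grade rate in 7.1, on an assumed 0 to 10 non-evaluable men, and on their loss being unrelated to grade.

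The matter deserves correction because it concerns participants' rights and costs almost nothing to put right. It does not call the pilot's design or sample size into question.

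**What to change.** **Section 4.5.1.** Delete the CEUS cut-off. State that a subject may withdraw from the research part at any point, including before any remaining targeted core. In a separate sentence, state that data collected up to withdrawal are retained and used as Section 9.1 allows. Check the consent form against the new text.

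**Section 7.3, as a consequential clarification.** State that sensitivity and specificity use men with both SHI scores and a 12-core systematic biopsy result. List all other consented men with the reason, and state the status of the 5 controls.

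**Cost.** A few sentences in two sections, plus any matching change to the consent form. The downside is that the accuracy table may hold slightly fewer than 50 men.

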5.0 STUDY DRUG/THERAPY

5.1 Description

This is not a therapeutic trial. The only drug that will be administered is Definity, which is a microbubble ultrasound contrast agent. The risk of the procedure is the risk of an adverse reaction to Definity, which is considered minimal. Although the study participants may not benefit from the findings, future patients may benefit from development of a non-invasive imaging technique that can detect and characterize aggressive PCa. If successful, this technique may reduce the number of biopsy procedures performed for prostate cancer, and it will likely be used to guide a limited number of targeted biopsy cores into those areas that demonstrate imaging characteristics of aggressive prostate cancer.

